#### 1300 **8.1.2.2 Hyperglycemic/Ketotic Events**

1301 Hyperglycemia not associated with an Adverse Device Effect is only reportable as an adverse  
1302 event when one of the following four criteria is met:

- 1303 • the event involved DKA, as defined by the Diabetes Control and Complications Trial  
1304 (DCCT) and described below
- 1305 • evaluation or treatment was obtained at a health care provider facility for an acute event  
1306 involving hyperglycemia or ketosis
- 1307 • blood ketone level  $\geq 1.0$  mmol/L and communication occurred with a health care provider  
1308 at the time of the event

1309     • blood ketone level  $\geq 3.0$  mmol/L, even if there was no communication with a health care  
1310       provider

1311  
1312   Hyperglycemic events are classified as DKA if the following are present:

1313     • Symptoms such as polyuria, polydipsia, nausea, or vomiting;  
1314     • Serum ketones  $>1.5$  mmol/L or large/moderate urine ketones;  
1315     • Either arterial blood pH  $<7.30$  or venous pH  $<7.24$  or serum bicarbonate  $<15$ ; and  
1316     • Treatment provided in a health care facility

1317  
1318 **8.1.3 Relationship of Adverse Event to Study Device**

1319   The study investigator will assess the relationship of any adverse event to be related or unrelated  
1320   by determining if there is a reasonable possibility that the adverse event may have been caused  
1321   by the study device. Note that this assessment will be made for both the investigational device  
1322   (AHCL system) and the commercially available system (670G 3.0).

1323  
1324   To ensure consistency of adverse event causality assessments, investigators should apply the  
1325   following general guideline when determining whether an adverse event is related:

1326     • **Unrelated:** The AE is clearly not related to a study drug/device and a likely alternative  
1327       etiology exists such as an underlying disease, environmental or toxic factors or other  
1328       therapy.

1329     • **Unlikely Related:** The AE does not follow a reasonable temporal sequence during or  
1330       after use of study drug/device and a more likely alternative etiology exists such as an  
1331       underlying disease, environmental or toxic factors, or other therapy.

1332     • **Possibly Related:** The AE occurred in a reasonable time during or after use of study  
1333       drug/device; but could be related to another factor such as an underlying disease,  
1334       environmental or toxic factors, or other therapy; and there is a possible, though weak,  
1335       scientific basis for establishing a causal association between the AE and the study  
1336       drug/device.

1337     • **Probably Related:** The AE occurred in a reasonable time during or after use of study  
1338       drug/device; is unlikely to be related to another factor such as an underlying disease,  
1339       environmental or toxic factors, or other therapy; and there is a plausible, though not  
1340       strong, scientific basis for establishing a causal association between the AE and the study  
1341       drug/device.

1342     • **Definitely Related:** The AE occurred in a reasonable time during or after use of study  
1343       drug/device; cannot be explained by another factor such as an underlying disease,  
1344       environmental or toxic factors, or therapy; and there is a strong scientific basis for  
1345       establishing a causal association between the AE and the study drug/device.

1346     • **Not Assessable:** Causality of an adverse event cannot be judged because information is  
1347       insufficient or contradictory, and which cannot be supplemented or verified.

1348  
1349 **8.1.4 Intensity of Adverse Event**

1350   The intensity of an adverse event will be rated on a three point scale: (1) mild, (2) moderate, or  
1351       (3) severe. It is emphasized that the term severe is a measure of intensity: thus a severe adverse  
1352       event is not necessarily serious. For example, itching for several days may be rated as severe, but  
1353       may not be clinically serious.

1354     • MILD: Usually transient, requires no special treatment, and does not interfere with the  
1355        participant's daily activities.  
1356     • MODERATE: Usually causes a low level of inconvenience or concern to the  
1357        participant and may interfere with daily activities, but is usually ameliorated by simple  
1358        therapeutic measures.  
1359     • SEVERE: Interrupts a participant's usual daily activities and generally requires  
1360        systemic drug therapy or other treatment.

1361  
1362 **8.1.5 Coding of Adverse Events**

1363     Adverse events will be coded using the MedDRA dictionary. The Medical Monitor will review  
1364        the investigator's assessment of causality and may agree or disagree. Both the investigator's and  
1365        Medical Monitor's assessments will be recorded. The Medical Monitor will have the final say in  
1366        determining the causality.

1367  
1368 **8.1.6 Outcome of Adverse Event**

1369     The outcome of each reportable adverse event will be classified by the investigator as follows:

1370     • RECOVERED/RESOLVED – The participant recovered from the AE/SAE without  
1371        sequelae. Record the AE/SAE stop date.  
1372     • RECOVERED/RESOLVED WITH SEQUELAE – The event persisted and had stabilized  
1373        without change in the event anticipated. Record the AE/SAE stop date.  
1374     • FATAL – A fatal outcome is defined as the SAE that resulted in death. Only the event  
1375        that was the cause of death should be reported as fatal. AEs/SAEs that were ongoing at  
1376        the time of death; however, were not the cause of death, will be recorded as “resolved” at  
1377        the time of death.  
1378     • NOT RECOVERED/NOT RESOLVED (ONGOING) – An ongoing AE/SAE is defined  
1379        as the event was ongoing with an undetermined outcome.  
1380        ◆ An ongoing outcome will require follow-up by the site in order to determine the final  
1381        outcome of the AE/SAE.  
1382        ◆ The outcome of an ongoing event at the time of death that was not the cause of death,  
1383        will be updated and recorded as “resolved” with the date of death recorded as the stop  
1384        date.  
1385     • UNKNOWN – An unknown outcome is defined as an inability to access the participant or  
1386        the participant's records to determine the outcome (for example, a participant that was lost  
1387        to follow-up).

1388     If any reported adverse events are ongoing when a participant completes the study (or  
1389        withdraws), adverse events classified UADEs will be followed until they are either resolved,  
1390        or have no prospect of improvement or change, even after the subject has completed all  
1391        applicable study visits/contacts. For all other adverse events, data collection will end at the  
1392        time the participant completes the study. Note: participants should continue to receive  
1393        appropriate medical care for an adverse event after their participation in the study ends.

1395 **8.2 Reportable Device Issues**

1396 All UADEs and ADEs as defined in Section 8.1.1 will be reported on both a device issue form  
1397 and AE form, except for skin reactions from CGM sensor placement or pump infusion set  
1398 placement that are not severe and/or require treatment.

1399  
1400 Device complaints and device malfunctions for the investigational device will be reported except  
1401 in the following circumstances. These occurrences are expected and will not be reported on a  
1402 Device Issue Form assuming criteria for a UADE or ADE have not been met:

- 1403 • CGM sensor lasting fewer days than expected per manufacturer
- 1404 • CGM tape adherence issues
- 1405 • Pump infusion set occlusion (including tubing and cartridge) not leading to ketosis  $\geq 0.6$   
1406 mmol/L or in the absence of checking for blood ketones, blood glucose  $>350$  mg/dL  
1407 (19.4 mmol/L); and not requiring an intervention other than replacing the tubing and/or  
1408 cartridge
- 1409 • Battery lifespan deficiency due to inadequate charging or extensive wireless communication
- 1410 • Intermittent device component disconnections/communication failures not requiring  
1411 system replacement or workaround/resolution not specified in user guide/manual.
- 1412 • Device issues clearly addressed in the user guide manual that do not require additional  
1413 troubleshooting

1414  
1415 **8.3 Pregnancy Reporting**

1416 If pregnancy occurs, the participant will be discontinued from the study. The occurrence of  
1417 pregnancy will be reported on an AE Form.

1418  
1419 **8.4 Timing of Event Reporting**  
1420 SAEs possibly related to an investigational device or study participation and UADEs must be  
1421 reported to the Coordinating Center within 24 hours of the site becoming aware of the event.  
1422 This can occur via phone or email, or by completion of the online serious adverse event form and  
1423 device issue form if applicable. If the form is not initially completed, it should be completed as  
1424 soon as possible after there is sufficient information to evaluate the event. All other reportable  
1425 ADEs and other reportable AEs should be submitted by completion of the online form within  
1426 seven days of the site becoming aware of the event.

1427  
1428 The Coordinating Center will notify all participating investigators of any adverse event that is  
1429 serious, related, and unexpected. Notification will be made within 10 days after the Coordinating  
1430 Center becomes aware of the event.

1431  
1432 Each principal investigator is responsible for reporting serious study-related adverse events and  
1433 abiding by any other reporting requirements specific to his/her Institutional Review Board or  
1434 Ethics Committee.

1435  
1436 Upon receipt of a UADE report, the Coordinating Center will investigate the UADE and if  
1437 indicated, report the results of the investigation to the sites' IRBs, and the FDA within ten  
1438 working days of the Coordinating Center becoming aware of the UADE per 21CFR 812.46(b)  
1439 (2). The Medical Monitor must determine if the UADE presents an unreasonable risk to  
1440 participants. If so, the Medical Monitor must ensure that all investigations, or parts of

1441 investigations presenting that risk, are terminated as soon as possible but no later than 5 working  
1442 days after the Medical Monitor makes this determination and no later than 15 working days after  
1443 first receipt notice of the UADE.

1444  
1445 Device malfunctions will be handled by the Coordinating Center.  
1446

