##### 569 **Continuous Glucose Monitoring**

570 Potential risks associated with CGM:

571 • Slight discomfort at the time of insertion of CGM (common)

572 • Slight bruising at the site of insertion (unlikely)

573 • Bleeding at insertion site (common)

574 • Infection at the site of insertion (rare)

575 • Allergic reaction to the CGM sensor adhesive material (common)

576

577 If a skin reaction is classified as severe (the observation is noticeable and bothersome to

578 participant and may indicate infection or risk of infection or potentially life-threatening allergic

579 reaction), an adverse event form will be completed.

580

Risks with Infusion Sets	Prevention and Mitigation

Risks with infusion sets may include:
 
 
• Localized infection
 
• Skin irritation/redness
 
• Bruising
 
• Discomfort/pain
 
• Bleeding
 
• Irritation
 
• Rash
 
• Hyperglycemia secondary to infusion set occlusion or infusion site failure
 
• Hyperglycemia secondary to site falling off
 
• Anxiety associated with insertion
 
	
Prevention and mitigation include:
 
 
• Follow the provided user guides for insertions and care of infusion sets.
 
• If an infusion site becomes irritated or inflamed, the infusion set should be removed and another placed in a new location.
 
• In case of hyperglycemia secondary to infusion set occlusion, remove current infusion set and replace with new infusion set and give correction insulin if directed with syringe.
 
• Follow the provided user guides for insulin pump management.
 
• Training prior to study on device use and diabetes management principles and told to call with problems.
 

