### 1264 **8.1.2 Reportable Adverse Events**

1265 For this protocol, a reportable adverse event includes any untoward medical occurrence that  
1266 meets one of the following criteria:

- 1267 1. An SAE
- 1268 2. An ADE as defined in Section 8.1.1, unless excluded from reporting in Section 8.2
- 1269 3. An AE as defined in Section 8.1.1 occurring in association with a study procedure
- 1270 4. An AE as defined in Section 8.1.1 which leads to discontinuation of a study device for two or  
1271 more hours
- 1272 5. Hypoglycemia meeting the definition of severe hypoglycemia as defined below
- 1273 6. Diabetic ketoacidosis (DKA) as defined below or in the absence of DKA, hyperglycemia or  
1274 ketosis event meeting the criteria defined below

1275

1276 Hypoglycemia and hyperglycemia not meeting the criteria below will not be recorded as adverse  
1277 events unless associated with an Adverse Device Effect. Skin reactions from sensor adhesive  
1278 placement are only reportable if severe and/or required treatment.

1279

1280 Pregnancy occurring during the study will be reported as an AE (see Section 8.3).

1281

1282 All reportable AEs—whether volunteered by the participant, discovered by study personnel  
1283 during questioning, or detected through physical examination, laboratory test, or other means—  
1284 will be reported on an AE form online. Each AE form is reviewed by the Medical Monitor to  
1285 assess safety and to verify the coding and the reporting that is required.

1286

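### As printed, the skin-reaction exemption in Protocol 8.2 makes needing treatment a ground for not reporting, which contradicts 8.1.2 for non-severe treated sensor reactions

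*Protocol*

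**What the plan says.** Four places in the protocol bear on when a skin reaction is reported.

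- **8.2 Reportable Device Issues** requires all adverse device effects, anticipated or not, to go on a device issue form "and AE form, except for skin reactions from CGM sensor placement or pump infusion set" "placement that are not severe and/or require treatment".
- **8.1.2 Reportable Adverse Events** states the rule from the other side, for sensor adhesive only: such reactions from "placement are only reportable if severe and/or required treatment". Item 2 of the same section lists as reportable "An ADE as defined in Section 8.1.1, unless excluded from reporting in Section 8.2". The definition of an adverse device effect in 8.1.1 carries the same deferral to 8.2.
- **1.4, under Continuous Glucose Monitoring**, gives a trigger for severe reactions: "If a skin reaction is classified as severe (the observation is noticeable and bothersome to" the participant, with possible infection or serious allergy, "reaction), an adverse event form will be completed". It does not mention treatment.
- **8.1.4 Intensity of Adverse Event** places moderate below severe and describes a moderate event as one that causes low-level inconvenience or concern to the "participant and may interfere with daily activities, but is usually ameliorated by simple" therapeutic measures.

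**The concern.** In 8.1.2, needing treatment brings a sensor reaction into reporting. In the printed words of 8.2, needing treatment takes it out. A site that follows the cross-references from 8.1.1 or from item 2 of 8.1.2 ends at the 8.2 sentence, so the clearer rule in 8.1.2 does not settle the matter by its own terms.

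These forms feed the counts of adverse events and of events meeting the adverse device effect definition (Protocol 10.8, SAP 8.3) and the tabulation of device issues (Protocol 10.14.1, SAP 14.1). SAP 8.1 takes its definitions from the protocol and does not resolve the point. With about seven sites, the counts could depend on which sentence each site follows. The Medical Monitor reviews submitted adverse event forms, so a form that was never filed would not come to light through that review.

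**Working it through.** No arithmetic applies. The check sets the rules side by side for the four possible reactions: severe or not, treated or not.

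The 8.2 phrase can be read in four ways:

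- A: exempt if non-severe and treated.
- B: exempt if non-severe, or if treated (the inclusive sense of and/or).
- C: exempt if neither severe nor treated (the negation covers the whole phrase).
- D: exempt unless both severe and treated.

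| Sensor reaction | 8.1.2 | 8.2, A | 8.2, B | 8.2, C | 8.2, D |
|---|---|---|---|---|---|
| Severe, treated | reportable | not exempt | exempt | not exempt | not exempt |
| Severe, untreated | reportable | not exempt | not exempt | not exempt | exempt |
| Non-severe, treated | reportable | exempt | exempt | not exempt | exempt |
| Non-severe, untreated | not reportable | not exempt | exempt | exempt | exempt |

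1. **The non-severe treated row.** 8.1.2 makes it reportable. Three of the four readings of 8.2 exempt it; only C does not.
2. **Overall agreement.** C is the only reading that matches 8.1.2 in every row. It is probably what was meant, since 8.1.2 uses nearly the same phrase in positive form, but 8.2 does not state it.
3. **Is the row occupied?** By the 8.1.4 scale a mild event needs no special treatment, so mild and treated is close to empty. Moderate and treated is a normal combination under 8.1.4, and that is the case at issue.
4. **Section 1.4.** It requires a form in the two severe rows and is silent on the two non-severe rows. It therefore takes no side on the non-severe treated case. It conflicts with 8.2 only under B (severe, treated) and D (severe, untreated).
5. **Infusion-set reactions.** The 8.1.2 sentence names only sensor adhesive, so it does not contradict 8.2 here. But 8.2 is then the only skin-reaction rule that names infusion-set reactions, and its wording is the defective one.

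**The case against.** The strongest reply is that the intent is obvious. A rule that drops a reaction because it needed treatment would reverse 8.1.2, and nobody is likely to have meant that. Under reading C the two sections agree for sensor reactions. This stands as an account of how the wording arose and keeps the point small. It does not remove the point, because 8.2 is an operative form-completion instruction to which two other places defer, and its printed words point the other way.

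A second reply is that little rests on these counts. This stands almost entirely. Of the tabulated event outcomes in SAP 8.3, only severe hypoglycemia and ketoacidosis are compared between arms. Reactions that are serious, or that lead to stopping a study device for two hours or more, are reportable under items 1 and 4 of 8.1.2 in any case.

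Three stronger readings are tempting but unsupported:

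- A reader might infer a three-way conflict that includes 1.4. That section says when a form is completed for a severe reaction, not that it is completed only then, so it does not conflict on non-severe treated reactions.
- A reader might infer that the affected group is sizeable because 1.4 lists allergic reaction to the sensor adhesive as common. That label covers all such reactions and gives no frequency for those that were non-severe and treated.
- A reader might infer bias between the systems. Protocol 1.3 says the sensor and infusion set are the same in both, and each participant uses both systems, so a site's reading would ordinarily apply to both periods.

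**Conclusion.** The inconsistency between 8.1.2 and 8.2 is real but minor. As printed, a non-severe treated sensor reaction is reportable under one and exempt under the other, and the harmonising reading has to be supplied by the reader.

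The effect is confined to the completeness and cross-site consistency of the adverse event, adverse device effect and device issue counts. The co-primary outcomes and the sample size do not depend on it, and the between-arm contrast is not materially affected. Its size cannot be determined, because the documents give no frequency for treated non-severe skin reactions and do not show how sites read the sentence.

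The conclusion assumes that the 8.2 exception removes the adverse event form as well as the device issue form. That is how 8.1.1 and item 2 of 8.1.2 treat it. The between-arm statement assumes that each site keeps one reading across both periods.

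**What to change.** Reword the 8.2 exemption to cover skin reactions *that are not severe and do not require treatment*. Extend the 8.1.2 sentence to name infusion-set as well as sensor reactions, so that both sections state one reporting rule.

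Align 1.4 for consistency only: refer to the same rule, and reconcile its description of a severe skin reaction with the intensity scale in 8.1.4, from which it differs.

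The cost is one phrase in 8.2, a few words in 8.1.2 and 1.4, and a matching line in the form instructions, which are not among the documents. The SAP revision history puts version 1.1 in the follow-up stage, so rewording alone would not recover forms already left unfiled. A short clarification to sites, with one query about treated skin reactions, would make the existing counts consistent.

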	
 
Human Factors and Diabetes Technology Attitude Surveys
 
 
Run-In Period (2-8 weeks)
 
Pump Run-In (670G 3.0 HCL)
 
Eligible participants will use the study 670G 3.0 HCL pump during the run-in. Participants who were pump users at screening may skip the Pump Run-In period (but must participate in the Pump+CGM Run-In period) per investigator discretion. 670G auto mode users may use the 670G pump in auto mode.
 
Standardized pump training will be provided to study participants and their diabetes care partners (for participants <18 years old). The study team will assist the participant in study pump infusion site initiation and will start the participant on the study pump. For current pump users, the study pump will be programmed with the participant's usual basal rates and pump parameters. The participant's personal pump will be removed. Participants may continue to use their personal CGM if applicable.
 
The pump will be used for at least two weeks during Pump Run-In, with the option of repeating Pump Run-In for an additional two weeks per investigator discretion. Contact will be made each week with additional contacts as needed. Prior to each contact, participants will be asked to upload device data for study staff to review.
 
After completion of Pump Run-In, participants will proceed to use the study CGM along with the study 670G 3.0 HCL pump during the Pump+CGM Run-In period.
 
Pump+CGM Run-In (670G 3.0 HCL + Guardian Sensor (3))
 
All participants must complete a two-week run-in period with the use of the study pump and CGM before being randomized into the crossover trial. During Pump+CGM Run-In, the predictive low glucose suspend feature will be turned on and auto mode will be off (i.e. manual mode). Participants who were 670G auto mode users at screening may use the pump in auto mode.
 
Standardized device training will be provided to study participants and their diabetes care partners (for participants <18 years old). Personal pumps and CGMs will be removed during the Pump+CGM Run-In period as applicable.
 
Contact will be made each week with additional contacts as needed. Prior to each contact, participants will be asked to upload device data for study staff to review.
 
Run-In Assessment
 
Successful completion of Pump Run-In is per investigator discretion. Pump Run-In may be repeated once.

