## 782 **Chapter 3: Run-in Phase**

### 783 **3.1 Introduction**

784 There are two parts of the run-in phase:

- 785 1) Pump Run-In (670G 3.0 HCL)
- 786 2) Pump+CGM Run-In (670G 3.0 HCL + Guardian Sensor (3))

787 The length of the run-in phases may vary depending on prior experience with a 670G pump, the  
 788 number of CGM hours collected during run-in, and how quickly participants become  
 789 comfortable using the study pump and CGM according to Table 5. Pump and CGM Run-In  
 790 Criteria below.

791

792 **Table 5. Pump and CGM Run-In Criteria**

	Pump Run-In: -670G 3.0 HCL -Two weeks, repeat if needed	Pump+CGM Run-In: -670G 3.0 HCL + Guardian Sensor (3) -Two weeks, repeat if needed -Auto mode off for non-670G auto mode users, PLGS on	
Pump Users	Optional (Complete per investigator discretion)	Required	Must have CGM data for at least 80% of the possible time during the prior 14 days and average BGM test 3x/day.
Non-Pump Users	Required	Required	Must have CGM data for at least 80% of the possible time during the prior 14 days and average BGM test 3x/day.

793

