### 794 **3.2 Pump Run-In – 670G 3.0 HCL**

795 Eligible participants will use the study 670G 3.0 HCL pump during the Pump Run-In period.  
 796 Participants who were current pump users at screening may skip the Pump Run-In period per  
 797 investigator discretion. Participants using the 670G in auto mode at screening may use the 670G  
 798 3.0 HCL pump in auto mode.

799

800 Standardized pump training will be provided using a training checklist to study participants and  
 801 their diabetes care partners (for participants <18 years old). Additional topics may include but  
 802 are not limited to: infusion site initiation, cartridge/priming procedures, setting up the pump,  
 803 changing batteries, and navigation through menus. The study team will assist the participant in  
 804 study pump infusion site initiation and will start the participant on the study pump. For current  
 805 pump users, the study pump will be programmed with the participant's usual basal rates and  
 806 pump parameters. Additionally, important differences between the study pump and personal  
 807 pumps such as calculation of insulin on board and correction boluses will also be discussed. The  
 808 participant's personal pump will be removed. Participants may continue to use their personal  
 809 CGM if applicable.

810

811 The pump will be used for at least two weeks during the Pump Run-In, with the option of  
 812 repeating the Pump Run-In for an additional two weeks per investigator discretion. A contact  
 813 will be made each week with additional contacts as needed. Prior to each contact, participants

814 will be asked to upload device data for study staff to review. The visit and contact schedule  
815 during the run-in is summarized in Table 1. Schedule of Visits and Procedures during Screening  
816 and Run-In.

817  
818 After completion of the Pump Run-In, participants will proceed to use the study CGM along with  
819 the study 670G 3.0 HCL pump during the Pump+CGM Run-In period on the same day.  
820

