### 1132 **6.3.2 Pump Failure**

1133 In the event of a pump failure, the participant will be instructed to use their personal insulin  
1134 regimen until the problem can be resolved. Reportable events are described in Chapter 8:.

1135

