1792 • Age: as a continuous variable and in two age groups: 14- $<$ 21 and 21- $<$ 30 years old  
1793 • Baseline HbA1c: as a continuous variable and in two groups: HbA1c  $\leq$ 8.5% and  $\geq$ 8.6%  
1794 • Insulin method/CGM: 670G user, injection user with CGM, injection user without CGM,  
1795 pump user with CGM, pump user without CGM  
1796 • T1D duration as a continuous variable  
1797 • Sex  
1798 • Race/ethnicity  
1799 • Random C-peptide level  
1800 Beyond above assessment for interactions, the primary and secondary analyses also will also be  
1801 conducted separately in the two age groups and the two HbA1c groups, in addition to the CGM  
1802 metrics considered as safety outcomes. Analyses will only be replicated within these subgroups  
1803 for efficacy outcomes where p-values are being computed.  
1804  
1805 **10.13 Multiple Comparison/Multiplicity**  
1806 For the primary analyses, the intervention will be deemed effective only if the null hypotheses  
1807 for both co-primary outcomes are rejected. The type 1 error is therefore not inflated and there  
1808 will be no correction for multiple comparisons.  
1809  
1810 For the secondary analyses, the false discovery rate will be controlled using the adaptive Two  
1811 Stage Benjamini-Hochberg procedure with  $<$ 0.05 as the threshold for statistical significance.  
1812  
1813 **10.14 Additional Tabulations and Analyses**  
1814 **10.14.1 Device Issues and Tabulations**  
1815 All reported device issues will be tabulated regardless of whether they were associated with  
1816 adverse events.  
1817  
1818 Detailed tabulations will include frequency of use of the system, discontinuation rate, and reasons  
1819 for discontinuation.  
1820  
1821 The amount of auto mode system use and CGM use will be calculated over each treatment  
1822 period. Similar repeated measures least squares regression models as described for the co-  
1823 primary outcomes will be used to compare the percentage of time of CGM use and auto mode

1824 use between the two periods. Monthly values for auto mode use and CGM use also will be  
1825 reported.

1826

1827 **10.14.2 Analysis of Quality of Life Data**

1828 Quality of life data collected during study assessments will be scored based on established  
1829 procedures and descriptive statistics (e.g., mean, range) will be calculated for each questionnaire  
1830 at each time point and across treatment groups. Similar models as described above for the  

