## 463     14. Additional Tabulations and Analyses

### 464     14.1 Device Issues

465     All reported device issues will be tabulated regardless of whether they were associated with  
466     adverse events. Separate listings will be provided for pre-randomization events and for events  
467     occurring during each treatment arm. For each device issue, the following information will be  
468     listed:

- 469             • Onset date
- 470             • Type of device issue
- 471             • Description of the device issue

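### Protocol 8.2 states the general duty to report non-ADE device complaints and malfunctions only for the investigational device, so the device-issue listings in SAP 14.1 may not be like for like between AHCL and the 670G 3.0

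*Protocol*

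**What the plan says.** Protocol 8.2 contains two reporting rules. The first sends every UADE and ADE to both a device issue form and an AE form, apart from minor skin reactions. The second deals with complaints and malfunctions that do not reach that level: "Device complaints and device malfunctions for the investigational device will be reported except" in a list of expected circumstances, such as short sensor life, tape problems and uncomplicated occlusions.

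The term investigational device is explained elsewhere. Protocol 8.1.3 and 8.5.1 attach it to the AHCL system, and 8.1.3 contrasts it with the commercially available 670G 3.0. Protocol 6.1.1 describes the 670G 3.0 as approved and unmodified.

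Protocol 6.3.2, on pump failure, is not limited to one pump. It has the participant fall back on a personal "regimen until the problem can be resolved. Reportable events are described in Chapter 8".

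The output rule is the same in Protocol 10.14.1 and SAP 14.1: "All reported device issues will be tabulated regardless of whether they were associated with" adverse events. SAP 14.1 then adds the split, in two consecutive lines: "adverse events. Separate listings will be provided for pre-randomization events and for events" and "occurring during each treatment arm. For each device issue, the following information will be" listed, namely onset date, type and description. Protocol 10.11 and SAP 11 put device issues among the data that the DSMB reviews about every six months.

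**The concern.** A listing by treatment arm invites the reader to set one arm beside the other. That is fair only if both arms were collected under the same rule. Here the stated rule for non-ADE issues names one of the two systems, and neither document tells the reader of the listing so.

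The pre-randomization listing raises the same question. Under Protocol 3.2, "Eligible participants will use the study 670G 3.0 HCL pump during the Pump Run-In period", and 3.1 keeps the same pump for the CGM run-in. That listing therefore covers a phase in which the only study pump is the one for which 8.2 states no complaint duty.

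At stake is the reading of a descriptive safety output, and of the same data at the DSMB. No hypothesis test is involved.

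**Working it through.** The documents give no device-issue rates and there is no plan figure to reproduce. The check is therefore a comparison of texts.

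**Where the protocol means both systems, it says so.**
- 8.1.1 applies the ADE definition for reporting to the 670G 3.0 as well as to AHCL.
- 8.1.3 requires the causality assessment for both.

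**Where it deals with non-ADE complaints, it does not.**
- 8.2 names the investigational device only.
- The complaint definition in 8.1.1 is also worded around an investigational device, though it adds an alternative about device performance. It carries no extension to the 670G 3.0 of the kind given for ADEs.
- 6.3.2 refers any pump failure to Chapter 8. For a 670G 3.0 failure without an ADE, Chapter 8 then states no complaint duty.

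**Device-neutral text that reaches the 670G 3.0.**
- 5.1.5.1 and 5.1.5.2 have device issues assessed at contacts and follow-up visits in both crossover periods. This prompts an assessment; 8.2 is the section that decides what is reported.
- 5.1.7 has device issues recorded at an early termination visit, whichever pump is in use. This is a recording instruction, but only for participants who leave early.
- Run-in has neither. Chapter 3 and Table 1 call for AE assessment and do not mention device issues.

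**Shared components.** Protocol 1.3 says that the sensor and infusion set are common to both systems. The Investigational Device row of the Protocol Summary includes the Guardian Sensor (3), whereas 6.1.2 says that the sensor is not investigational. Whether 8.2 covers a sensor complaint during 670G 3.0 use therefore depends on which section is followed.

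**Direction under a literal reading.** ADE-linked issues are captured for both systems. Non-ADE issues outside the exceptions are captured for AHCL and, apart from the device-neutral text above, not required for the 670G 3.0. The AHCL listing is then the fuller one.

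**Illustration, on assumptions that are not in the documents.** Suppose that each system has the same true number N of issues outside the exceptions, that a share a of them is ADE-linked, and that sites report for the 670G 3.0 only what 8.2 requires. AHCL shows N, the 670G 3.0 shows aN, and the ratio is N / (aN) = 1/a:
- a = 50%: 1/0.50 = 2 to 1
- a = 25%: 1/0.25 = 4 to 1
- a = 10%: 1/0.10 = 10 to 1

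This shows the mechanism. It is not an estimate, because neither a nor site practice is given.

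**The case against.** The strongest reply is that 8.2 is loosely worded and that collection was meant to be the same for both systems. Several places support this. Device issues are assessed in both periods. 5.1.7 is neutral. The malfunction definition in 8.1.1 speaks of any device. 8.4 routes malfunctions to the coordinating center without naming a pump. SAP 14.1 plans a pre-randomization listing, when only the 670G 3.0 is in use. This stands as evidence of possible intent. It does not supply the missing reporting rule, and the pre-randomization listing could be filled by ADE-linked issues alone.

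A second reply is that the narrower duty may be deliberate: fuller complaint capture is defensible for the experimental pump when the comparator is an approved, unchanged device. That also stands. It argues for telling the reader, not for leaving the listing unmarked.

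A third is that little depends on the listing. No rate, ratio or test is planned. Auto mode and CGM use are compared from device data by the same method in both arms (SAP 14.2). Any distortion would run against AHCL. All of this is accepted and sets the low priority.

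Three stronger readings are tempting and are not supported:
- That the 670G 3.0 has no device-issue reporting at all. The ADE rule covers it, and 5.1.7 applies to either pump.
- That the data were in fact collected unequally. The documents contain neither the form instructions nor site practice.
- That the gap can be sized from weeks of use on each pump. Run-in issues are listed separately from the arms in SAP 14.1, and exposure time without an event rate measures no distortion.

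**Conclusion.** The point holds as a difference in the stated rules. The general duty to report non-ADE complaints and malfunctions is written for AHCL only, and for the 670G 3.0 the remaining text is assessment during the crossover and recording at early termination. The position of sensor complaints during 670G 3.0 use is unclear.

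If sites followed 8.2 literally, the SAP 14.1 listings and the DSMB's device-issue data would be more complete for AHCL and would tend to make it look worse. The conclusion rests on that condition. The size cannot be derived. The co-primary, secondary, ADE/UADE, severe hypoglycemia and DKA analyses are untouched. This is a cheap improvement to a descriptive output and no threat to the trial's conclusions.

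**What to change.** If the rule can still be set before the forms are collected, state in 8.2 that complaint and malfunction reporting, with the same exceptions, applies to both study systems and their shared components, including during run-in. Reconcile the Protocol Summary and 6.1.2 on the status of the sensor. The cost is a sentence or two and a few more Device Issue Forms.

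If the narrower duty is deliberate, or forms already exist under it, a late amendment could leave the 670G 3.0 arm with two rules. SAP version 1.1 is marked as Follow-Up stage, so this case is likely. Then:
1. Check which device issues sites actually reported during 670G 3.0 use, in run-in and in the crossover.
2. In the SAP 14.1 listings, show ADE/UADE-linked issues separately from all others.
3. Only if the check shows that collection differed, add a footnote that non-ADE issues are not comparable between arms or with the pre-randomization listing. Give the DSMB the same note.

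The cost is the check, one extra column and, if needed, the footnote.
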